#### ***7.2.5 Short-term Follow-up Period: D7 to D14***

On D8 to D14 all assessments should be performed at the same time of day as the D7 assessments were performed. The following study assessments and procedures will be performed:

- Check patient survival
- Confirm whether patient is still in hospital
- Confirm whether patient is in the ICU. Patients still requiring intensive care who are transferred to another hospital or healthcare ICU facility prior to D14 will be followed up to assess the days in ICU at D28
- Check whether the patient is on ventilation (refer to Section 6.1.1 for definition of UAB). Patients still on positive pressure ventilation who are transferred to another hospital or healthcare facility prior to D14 will be followed up to assess the VFD outcome at D28
- Record SOFA scores
- Recording of vasoactive drugs and renal support
- ECG is taken on D7
- Vital signs (temperature, BP and HR) must be measured and recorded in the morning between 04:00 and 10:00 using the values closest to 10:00 (if these values are representative of the patient's condition). All vital sign assessments must be taken at the same time point whenever possible
- Haematology, biochemistry and urinalysis: Samples must be taken daily in the morning between 04:00 and 10:00 using the values closest to 10:00
- MxA, CD73 and PIM samples for central testing taken at the same time as on D6  $\pm 2$  hours
- Recording of concomitant medications and therapies
- Recording of AEs

### **7.2.6 Short-term Follow-up Period: D15 to D27**

- Check patient survival
- Confirm whether patient is still in hospital
- Confirm whether patient is in the ICU. Patients still requiring intensive care who are transferred to another hospital or healthcare ICU facility prior to D27 will be followed up to assess the days in ICU at D28
- Check whether the patient is on ventilation (refer to Section 6.1.1 for definition of UAB). Patients still on positive pressure ventilation who are transferred to another hospital or healthcare facility prior to D27 will be followed up to assess the VFD outcome at D28
- Record SOFA score only on D21
- Recording of vasoactive drugs and renal support
- Vital signs (temperature, BP and HR) must be measured and recorded in the morning between 04:00 and 10:00 using the values closest to 10:00 (if these values are representative of the patient's condition). All vital sign assessments must be taken at the same time point whenever possible
- Haematology, biochemistry and urinalysis: Samples must be taken daily in the morning between 04:00 and 10:00 using the values closest to 10:00
- Recording of concomitant medications and therapies
- Recording of AEs

### **7.2.7 Short-term Follow-up Period: Last Day in ICU**

These assessments will be done on the day the patient leaves the ICU, either on D28 or earlier, according to the clinical progress of the patient. If the patient is still in the ICU on D28, the next visit or telephone contact will be at D90. If a patient leaves the ICU before D28, the survival status and other endpoints must be assessed on D28.

The following should be done:

- Check patient survival
- Confirm whether patient is in the ICU/in hospital
- Check whether the patient is on ventilation
- Record SOFA scores
- Recording of vasoactive drugs and renal support
- Neutralising antibody sample taken for central testing
- Record pharmacoeconomic assessments (see Section 6.4)
- Physical examination of major body systems
- Vital signs (temperature, BP and HR) must be measured and recorded in the morning between 04:00 and 10:00 using the values closest to 10:00 (if these values are representative of the patient's condition). All vital sign assessments must be taken at the same time point whenever possible
- Haematology, biochemistry and urinalysis: samples must be taken in the morning between 04:00 and 10:00 using the values closest to 10:00
- Recording of concomitant medications and therapies
- Recording of AEs

### **7.2.8 Short-term Follow-up Period: D28**

These procedures apply to patients having left the ICU before D28 and for patients withdrawing from the study before D28.

- Check patient survival
- Confirm whether patient is in the ICU/in hospital
- Check whether the patient is on ventilation
- Record SOFA score, to the extent possible at the investigational site
- Recording of vasoactive drugs and renal support
- Physical examination, including vital signs if possible to be completed by the investigator
- Haematology, chemistry and urinalysis, if possible to perform at the investigational site
- Update pharmacoeconomic assessments (see Section 6.4)
- Recording of concomitant medications and therapies
- Recording of AEs and follow-up on previously reported AEs.

For patients withdrawing from the study, a sample should be taken for neutralising antibodies (see Section 7.2.11.1).

### **7.2.9 Long-term Follow-up Period: D90 and D180**

The study has a long-term follow-up period, with assessments at 3 (D90) and 6 months (D180) after the first dose of study drug was administered. The D90 assessment can be either a visit or telephone contact. For both D90 and D180 follow-up, there is a time window of +14 days.

- Check patient survival
- Recording of AEs if the Investigator considers there is a causal relationship with the study drug
- Report as SAE if the patient died.
- Confirm whether patient is in the ICU/in hospital
- Check whether the patient is on ventilation
- At D180 only: EQ-5D-3L, FEV1 and 6MWT (including ECG).

If it is not possible for the patient to attend a physical visit, as much information as possible, including QoL, should be obtained by phone.

### **7.2.10 Extended Long-term Follow-up: D360**

The study has an extended long-term follow-up period with an assessment at 12 months (D360) after the first dose of study drug was administered. There is a time window of ±14 days for this visit.

- Check patient survival
- Recording of AEs if the Investigator considers there is a causal relationship with the study drug
- Report as SAE if the patient died
- Confirm whether patient is in the ICU/in hospital

- Check whether the patient is on ventilation
- EQ-5D-3L, FEV1 and 6MWT (including ECG).

If it is not possible for the patient to attend a physical visit, as much information as possible, including QoL, should be obtained by phone.

### ***7.2.11 Early Termination Visit***

Patients who discontinue early from the study should, if possible, have an early termination visit. The procedures will vary depending on whether the patient withdrew on or before D28 (see Section 7.2.11.1) or after D28 (see Section 7.2.11.2). This visit should take place as soon as possible after it was learned that the patient will not be able to complete follow-up (see also Section 4.4).

#### ***7.2.11.1 Withdrawal Prior to D28***

For patients withdrawing on or before D28, procedures for the last day in the ICU should be followed. In addition, a sample should be taken for neutralising antibodies.

In the case of an ongoing AE, appropriate safety evaluations and/or additional tests may be performed at any time when clinically indicated at the discretion of the Investigator, until resolution or D28, whichever is first.

Any ongoing AEs should be followed up to resolution or D28, whichever is the sooner.

If the patient refuses to have any of the above assessments, or if the patient is lost to follow-up, then this should be noted in the e-CRF.

If a patient is lost to follow-up, wherever possible, mortality data will be sought from alternative sources, such as the patient's local physician or available national databases and all data obtained reported as SAEs.

#### ***7.2.11.2 Withdrawal after D28***

If a patient withdraws after D28, no further follow-up will be attempted. However, if a patient is lost to follow-up, wherever possible, mortality data will be sought from alternative sources, such as the patient's local physician or available national databases and all data obtained reported as SAEs.

## 8 STATISTICAL METHODS

The statistical considerations summarised in this section outline the plan for data analysis of this study.

Before unblinding/database lock, a separate Statistical Analysis Plan (SAP) will be finalised, providing detailed methods for the analyses outlined below. After the clinical parts of the study have been completed, a blinded review of the data will be undertaken according to the SAP. This review will make decisions regarding: the handling of missing data and data for withdrawn patients; the handling of countries recruiting only a small number of patients in the statistical analyses that include country effects; and the definition of the Per-Protocol Set (PPS) at the patient level. Any deviations from the planned analyses will be described and justified in the final integrated study report.

### 8.1 Study Patients

#### 8.1.1 Disposition of Patients

Disposition and reasons for discontinuation will be summarised for all patients together with study drug exposure and study duration by treatment group.

The number and percentage of patients entering and completing each phase of the study will be presented by treatment group. Reasons for withdrawal pre- and post-randomisation will also be summarised.

The disposition of patients will also include information on the number and percentage of patients who:

- completed study drug and follow-up
- withdrew from study drug but completed follow-up
- withdrew from study drug and from follow-up

#### 8.1.2 Protocol Deviations

Deviations from the protocol including violations of inclusion/exclusion criteria will be classified as “minor” or “major” in conjunction with the Sponsor and Medical Monitor. Major deviations from the protocol will lead to the exclusion of that patient from the PPS. Deviations will be defined prior to unblinding.

#### 8.1.3 Analysis Sets

The following analysis sets will be defined for statistical analysis:

The **Full analysis set (FAS)** will consist of all randomised and treated patients. The primary efficacy analyses will be based on this data set. Patients will be included in the analysis according to the treatment to which they were randomised.

The **Per-Protocol Set (PPS)** will consist of patients in the FAS excluding patients with major protocol violations. A list of major protocol violations relevant for excluding data from the PPS will be detailed in the SAP. The precise definition of the PPS at the patient level will be identified at the blinded data review meeting.

Statistical analyses for the primary and secondary endpoints will be performed on both the FAS and PPS.

The **safety set** will consist of all patients who receive at least one dose of study drug. All safety and tolerability analyses will be based on this analysis set. A patient who

receives the wrong treatment according to their randomisation will be analysed for safety and tolerability in the treatment group corresponding to the treatment received. Statistical analyses for the primary and secondary endpoints will be performed on both the FAS and PPS. The primary efficacy endpoint analysis will be based on the FAS; a secondary analysis will also be performed based on the PPS to assess the sensitivity of the analysis to the choice of analysis set. All safety analyses will be based on the safety set. Demographic and baseline characteristics will be evaluated for the FAS.

## **8.2 General Considerations**

All statistical tests will be two sided and will be performed at the significance level of 0.05, unless otherwise stated.

Continuous data will be summarised by treatment group using descriptive statistics (number, mean, median, standard deviation [SD], minimum and maximum). Categorical data will be summarised by treatment group using frequency tables (frequencies and percentages).

### **8.2.1 Analysis and Data Conventions**

#### *8.2.1.1 Definition of Baseline*

The baseline assessment, where relevant, will be the latest available valid pre-dose assessment.

#### *8.2.1.2 Visit Windows*

Assessments made outside of protocol-mandated windows will be displayed according to the e-CRF assessment recorded by the Investigator.

#### *8.2.1.3 Unscheduled Assessments*

Extra assessments (laboratory data or vital signs associated with non-protocol clinical visits or obtained in the course of investigating or managing AEs) will be included in listings, but not summaries. If more than one laboratory value is available for a given visit, the first valid observation will be used in summaries and all observations will be presented in listings. It is noted that invalid laboratory data will not be used (from haemolysed samples, mishandled samples, quantity not sufficient, or other conditions that would render values invalid).

#### *8.2.1.4 Missing Data Handling*

In general, data will not be imputed for the primary efficacy analysis or the safety analysis. For other efficacy analyses, where relevant, imputations will use the last observation carried forward method for patients in the analysis. Additional details will be given in the SAP.

Treatment by country interactions will be investigated and if any country has too few patients, a pooling strategy will be defined at the blinded data review, prior to unblinding.

The approach to multiplicity testing for the key secondary endpoints is explained in Section 8.5.2.1.1.

### **8.3 Demographics, Medical History, Baseline Characteristics and Concomitant Medications**

Baseline assessments will consist of those assessments carried out in the screening period and those carried out prior to the first dose of study drug on D1.

Demographic and baseline characteristics will be summarised by treatment group and overall. No formal statistical comparisons will be undertaken to compare treatment groups for any of these parameters.

Demographic data, medical history, concomitant disease and concomitant medication will be summarised by descriptive statistics (number, mean, SD, median, minimum and maximum) or frequency tables, overall and stratified by treatment.

A medication given prior to the first injection of study drug will be classified as a prior medication. A medication given with or after the first injection of study drug will be classified as concomitant. Prior medications continuing during the study will be labelled accordingly in the listings.

### **8.4 Treatment Compliance**

As the study drug is administered directly to the patient in the ICU, treatment compliance will not need to be measured.

### **8.5 Efficacy Analyses**

#### **8.5.1 Primary Efficacy Analysis**

##### *8.5.1.1 Hypotheses to Be Tested*

The following hypotheses will be tested:

- Null hypothesis  $H_0$ : the value of VFDsurv in the treatment group is equal to that in the placebo group
- Alternative hypothesis  $H_A$ : the value of VFDsurv in the treatment group is not equal to that in the placebo group

##### *8.5.1.2 Statistical Methods*

The primary composite endpoint includes death and days free of mechanical ventilation within 28 days among survivors. VFDs to D28 is defined as the number of calendar days during which the patient is ventilator-free including two UAB days to D28, assuming that a patient survives for at least two consecutive calendar days after initiating UAB.

For example: If a patient initiates UAB in the afternoon of D16 and survives to D28 that patient would be assigned a VFD value of 12. If a patient initiates UAB in the afternoon of D16 but dies in the afternoon of D25 they would be assigned a VFD value of 9. If a patient survives for more than 48 hours after initiating UAB but then requires assisted breathing (for any reason) before D28, the VFD value would be the total number of UAB days before D28 unless a period of assisted breathing was less than 24 hours and the purpose of assisted breathing was a surgical procedure. Patients who die without initiating UAB will be assigned a VFD value of 0 and patients who require more than 28 days of mechanical ventilation will also be assigned a VFD value of 0.

The non-parametric analysis of the primary composite endpoint VFDSurv is based on a scoring scheme with patients who do better getting a higher score. All patients who die before 28 days will be assigned a VFDSurv score of -1. For those patients who survive to D28 the VFDSurv score will be equal to the VFD value calculated according to the above definition.

The statistical analysis for group comparison of the primary endpoint will then be based on the van Elteren test adjusting for country, ARDS severity and key baseline characteristics. (Ref: Van Elteren 1960) The statistical methodology with regard to the scoring scheme is as set down in Finkelstein and Schoenfeld. (Ref: Finkelstein et al 1999) The primary analysis of this endpoint will be based on the FAS, with a sensitivity analysis based on the PPS providing supportive information. Each of these analyses will be undertaken at the two-sided significance level of 0.05.

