##### 8.5.2.1.1 Control of Multiplicity

Multiplicity will be controlled across the key secondary endpoints using a pre-specified hierarchy. The pre-specified hierarchy is:

1. All-cause mortality at D28
2. All-cause mortality at D90
3. All-cause mortality at D180
4. Mortality in ICU at D28
5. Mortality in hospital at D28

Statistical significance will be declared down to the first non-significant endpoint (based on a two-sided significance level of 0.05) in this hierarchy. All p-values at and below this level will be considered as providing supportive information only.

VFDsurv will also be considered as a secondary endpoint, although no formal p-value comparisons will be undertaken for that endpoint as patients who die will be excluded from such an analysis.

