## 8.10 Determination of Sample Size

For 90% power and a two-sided Mann–Whitney U-test at the significance level of 0.05, a total of 272 patients are required based on the following assumptions:

- mortality rate of 30% in the control group and 15% in the FP-1201-lyo group at D28
- 20% of patients survive but with zero ventilator-free days (VFDs) in the control group
- A mean difference (FP-1201-lyo minus control) of 3.0 days in mean ventilator-free days where patients who die are assigned a score of 0

However, assuming 5% of patients (16) drop-out and a further 4% (12) of the remaining patients will not be evaluable for the efficacy analysis, the study will randomise 300 patients to build in some flexibility around the assumptions listed above.

PASS software (Version 11; NCSS LLC, Kaysville, UT, USA) was used to calculate the required sample size for this study. Table 6 gives values for power based on this sample size and alternative values for the mortality rates in the two treatment groups with a total sample size of 300 (including 5% drop-outs and a further 4% non-evaluable patients). These calculations are based on the construction of two multinomial distributions according to the above assumptions and the associated non-parametric comparison of those distributions.

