### ***5.3.3.2 Days Free Of Mechanical Ventilation Evaluations***

The Total number of days free of Mechanical ventilation is derived from the Patient Status report recorded on each day during the 28 day period. Patients who die during this period will be assigned a value of zero. Defined rules are specified in Section 5.9.4, Appendix 4.

The definition used by site staff for unassisted breathing (UAB) and 'being ventilator free for the whole of the calendar day' as recorded in the CRF is given in the protocol.

This variable is not the same as the calculated Ventilation Free Days (VFD) endpoint which contributes to the VFDsurv primary efficacy endpoint as it requires 2 consecutive calendar days of UAB. If there are fewer than 2 consecutive days of UAB then VFD is assigned the value zero.

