### **7.2.3.2 Primary Efficacy Analysis - Ventilation Free Survival (VFDsurv)**

VFDsurv scores derived will be numerically summarised (excluding means and standard deviations) according to Treatment group (FP-1201-lyo/Placebo), Severity of ARDS (Moderate/Severe) and Overall. Statistical significance overall (Van Elteren p-values) will be displayed with the numerical summaries. Both FAS and PPS group analyses will be given (Table 14.2.2.1.1). Table 14.2.2.1.1 will also display secondary efficacy variables in the same manner, including Ventilation Free Days (VFD), Days Free of Organ Failure, Days Free of Renal Support, Days Free of Vasoactive Support, Days Free of Mechanical Ventilation, Number Of ICU Care Free Days, Number of ICU days and Number of Days In Hospital.

A frequency distribution (Table 14.2.2.2), together with Box and Whisker plots (Figures 14.2.1) of the VFDsurv scores will be presented by Treatment group and by Severity of ARDS for both FAS and PPS populations.

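### Deaths are treated inconsistently in the secondary ventilator-free-days variable: counted up to death, excluded, or scored 0, depending on the section

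*Protocol*

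**What the plan says.** - **Counted.** Protocol 8.5.1.2 defines VFD and gives two examples of unassisted breathing that starts on the afternoon of D16. The patient who survives to D28 gets 12. The one who "dies in the afternoon of D25 they would be assigned a VFD value of 9". Among deaths, 0 is given only to those who never started unassisted breathing. The same section sets the primary VFDsurv score to −1 for every death before 28 days and uses VFD only for survivors.
- **Excluded.** Protocol 8.5.2.1.1 lists VFDsurv as a secondary endpoint as well and says "no formal p-value comparisons will be undertaken for that endpoint as patients who die will be excluded from such an analysis".
- **Zero, in planning.** Protocol 8.10 assumes "A mean difference (FP-1201-lyo minus control) of 3.0 days in mean ventilator-free days where patients who die are assigned a score of 0". Table 6 footnote 3 and SAP 6.1.2 use the same rule.
- **Zero, for a neighbouring variable.** For actual days free of mechanical ventilation, SAP 5.3.3.2 says "Patients who die during this period will be assigned a value of zero", and SAP 6.2.4.2 applies the van Elteren test. SAP 5.3.3.2 also states that this variable differs from VFD.
- **Reported.** SAP 7.2.3.2 says that Table 14.2.2.1.1, which carries the primary result with its van Elteren p-value, "will also display secondary efficacy variables in the same manner, including Ventilation Free Days (VFD").
- **Derivation.** SAP 5.3.2 and 5.9.4 place the VFD scoring rules in Appendix 4, which is not in the text available for this review.

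**The concern.** VFD will stand beside the primary endpoint in the same table, and the three rules answer different questions. Counting days up to death credits a patient for coming off the ventilator and then dying. A rank test on that score can place a death above a survivor. Excluding deaths compares only survivors, a group shaped by treatment if the drug changes mortality; the design assumes that it halves it, from 30% to 15%. Scoring deaths 0 keeps every patient and matches the quantity used in sizing the trial.

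The documents also disagree on whether VFD is tested at all: the protocol sentence rules out a formal p-value and the SAP table implies one. If this is settled after unblinding, the choice could follow the result.

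**Working it through.** **Inputs** (Protocol 8.10 and the Table 6 row with 15% and 30% mortality and a 3.0-day difference), as shares of all patients:

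| | Active | Control |
|---|---|---|
| Dead by D28 | 0.15 | 0.30 |
| Alive, VFD 0 | 0.14 | 0.20 |
| Alive, VFD 1–28 | 0.71 | 0.50 |

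Table 6 gives 2.5% and 1.8% per day. This matches an even spread over days 1–28: 0.71/28 = 2.54% and 0.50/28 = 1.79%. The mean of 1 to 28 is 406/28 = 14.5.

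**1. Reproduce the plan's figures.** On the primary score (−1, 0, 1–28), the probability that an active patient does better, plus half the ties, is

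0.14×0.30 + 0.71×0.50 + ½×0.71×0.50 + ½×0.15×0.30 + ½×0.14×0.20 = 0.611.

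- The Noether formula gives N = (1.960 + 1.282)² / [3×(0.111)²] = 284.3.
- With the tie-corrected null variance and the variance under the alternative, N = 273.9, against the stated 272.
- Simulation (10,000 runs, 136 per arm) gives 89.5% power.
- 272/0.96 rounds up to 284, the Table 6 entry.
- Mean VFD with deaths = 0: 0.71×14.5 = 10.295 and 0.50×14.5 = 7.25. The difference is 3.045, against the stated 3.0.

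**2. Exclude deaths.** 10.295/0.85 = 12.11 and 7.25/0.70 = 10.36, a difference of 1.75 days. That is (3.045 − 1.755)/3.045 = 42% smaller than with deaths at 0. Two sensitivity checks:

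- If the zero-scored difference is set to exactly 3.0, the survivors-only figure is 10.25/0.85 − 7.25/0.70 = 1.70.
- SAP 6.1.2 words the 20% as a share of control survivors. Taken literally, that is 0.20×0.70 = 14% of control patients. The control mean is then 0.56×14.5 = 8.12, the active mean 11.12, and the survivors-only difference 11.12/0.85 − 8.12/0.70 = 1.48.

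**3. Count days to death.** Let m be the mean VFD of patients who die. The documents do not give it; assume that it is equal in both arms. The difference is (10.295 + 0.15m) − (7.25 + 0.30m) = 3.045 − 0.15m.

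| m | 0 | 2 | 5 | 9 |
|---|---|---|---|---|
| Difference (days) | 3.0 | 2.7 | 2.3 | 1.7 |

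**4. Medians.** SAP 6.2.3.2 and 7.2.3.2 omit means for the primary score, and VFD follows that format.

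- Deaths = 0: the active median is 9 (29% + 9×2.54% first exceeds 50%). Control has exactly 50% at zero, so its median lies between 0 and 1. The gap is 8 to 9 days.
- Survivors only: 12 against 9, a gap of 3 days.

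**5. Ranking under the counting rule.** Unassisted breathing from the afternoon of D16 and death on D25 counts D17–D25 = 9. By the same counting, a D28 survivor who starts on the afternoon of D20 gets D21–D28 = 8. A survivor ventilated throughout gets 0. The death outranks both.

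**The case against.** Four points on the other side carry weight.

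- **The worked example ranks correctly.** A reader might infer that the protocol's own example puts a death above a survivor. It does not: the survivor gets 12 and the patient who dies gets 9. The inversion follows only when the counting rule is applied to survivors with fewer than 9 days.
- **The planned effect is not ambiguous.** A reader might infer that the design effect slides from 3.0 to about 1.75 days, or that the sample size is in doubt. Every planning passage ties 3.0 days to deaths scored 0, and 272 reproduces. The 1.75 is a different quantity, a survivors-only mean.
- **Part of the conflict is labelling.** The exclusion sentence names VFDsurv, which scores deaths by definition, so it most plausibly means VFD. The SAP's zero rule in 5.3.3.2 belongs to a variable that it separates from VFD and handles clearly.
- **The programmer is directed to Appendix 4.** That appendix may already fix a rule, so it cannot be said that the SAP lacks one.

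It is also true that VFD is in neither testing hierarchy (Protocol 8.5.2.1.1, SAP 6.1.3) and that the table will not show means. These points limit the consequence. They do not remove the disagreement within the protocol between 8.5.1.2, 8.5.2.1.1 and 8.10, or the conflict between the protocol's bar on a p-value and the SAP's display.

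**Conclusion.** The inconsistency is real and confined to VFD as a secondary variable. It does not reach the primary endpoint: every death before 28 days scores −1, below every survivor, so the primary test, the 272 and its power of about 90% stand.

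The rule chosen changes the secondary result materially. Under the planning distributions, the mean difference is about 3.0 days with deaths at 0 and about 1.75 among survivors (1.5 on the literal SAP reading of the 20%). With days counted to death, it runs from 3.0 down to 1.7 as the mean VFD of patients who die goes from 0 to 9. These figures assume an even spread over days 1–28 and, for the last rule, equal m in both arms. They show sensitivity under design assumptions and do not predict the trial result.

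No formal secondary claim rests on VFD. Still, a rank test under the stated counting rule could favour deaths over survivors, and correcting it is cheap. It should be settled before unblinding.

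**What to change.** 1. In both documents, score VFD as 0 for any death by D28 when it is reported as a secondary variable. This matches Protocol 8.10, Table 6 footnote 3, SAP 6.1.2 and the SAP rule for days free of mechanical ventilation.
2. In Protocol 8.5.1.2, change the D25 example to VFD 0 (VFDsurv −1).
3. In Protocol 8.5.2.1.1, correct the label from VFDsurv to VFD. Delete the exclusion of deaths, or keep it only as a labelled survivors-only description without a p-value.
4. State in both documents whether VFD is tested, and make Table 14.2.2.1.1 agree.
5. Confirm that SAP Appendix 4 uses the same rule, and state the rule beside that table.

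The cost is wording in two protocol sections, a line or so in the SAP, and a check of the appendix. No new data are needed, and neither the primary analysis nor the sample size changes.
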